Once generated, documents that include the randomization sequence will be password protected to avoid inadvertent access by research staff involved in the enrollment process. Research staff will contact the project managers to randomize all participants using the randomization sequence provided by the biostatistician. The randomization process will be overseen by the project managers who will be notifying the research therapists of assigned

condition for specific participants at the completion of all baseline assessments. Randomization will occur once the baseline enrollment assessments are complete, which will take place no later than 60 days following the completion of the eligibility screening survey. Initiation of the study treatment condition (either PPMI or EUC) will occur immediately following randomization, when possible. Study sessions delivered via telephone or video chat should take place within one week of study enrollment and randomization for those in the PPMI condition and within two weeks of study enrollment and randomization for those in the EUC condition in order to provide enough time for all sessions to be completed within the 4-6-week treatment window.

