6.2.3 Blinding

For this study, participants will not be blind to the condition they are receiving given the fact that the PPMI condition and the EUC condition are of varying lengths (8 sessions vs. 2 sessions). Despite this, we are confident that the nature of the EUC condition (e.g. a study therapist providing education and support to those with chronic pain engaged in OUD treatment) will produce enough of a supportive effect to provide a strong test of the added benefits of PPMI above and beyond the care typically delivered in the community. Study therapists who deliver the condition will not be blind due to the fact that they will be delivering both conditions. Therapists will, however, be trained and instructed to provide a similar level of attention to each participant during the session, regardless of treatment condition.

Data collectors responsible for the collection of follow-up data (post-enrollment data) (i.e. research assistants, project managers, or other study staff) will remain blind to the treatment condition assignment to ensure accurate and unbiased collection of trial outcomes. It is important to note that the primary outcome of interest (retention on buprenorphine treatment over 3-months post enrollment) will be collected via participant self-report through weekly surveys. Therefore, study staff will not be directly involved in the collection of those outcome data. Longitudinal data of the primary outcome (retention on buprenorphine treatment over 12-months post enrollment) will be collected by research study staff via researcher administered interview, and therefore these study staff will remain blind to the assigned treatment condition. In the event that longitudinal data may need to be reviewed for accuracy and coding following collection through case consultation meetings, outcome adjudicators, including investigators or project consultants will be blind to condition assignment to ensure unbiased coding of data. Importantly, the data managers and data analysts will remain blind to study condition when conducting all analyses.

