9.2.1 Treatment Assignment Procedures

Details regarding how participants will randomly be assigned to one of the two study conditions (PPMI vs. EUC) are described above (see Section 5. “Study Conditions”, Section 6.2.2 “Enrollment, Baseline, and Randomization”, and Section 6.2.3 “Blinding”).

Randomization will be stratified by gender (biologically assigned male versus biologically assigned female at birth), past year use of heroin (yes/no), and veteran status (community/veteran). There is no sample size goal for each stratum, although strata assignment

and condition assignment will be monitored throughout the study to ensure an imbalance does not occur that could impact the ability to report on main study outcomes. Data on adherence to the intervention condition's protocol will be collected monthly by research staff and reviewed monthly by the PI/Project Managers. Adherence of participants will be evaluated by the Project Managers. If adherence falls below the expected rate, which might inhibit the ability of the study to test its primary hypotheses, the Project Managers will suggest a conference call for study investigators to discuss methods for improving adherence.

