9.5.1 Primary Outcome

The **primary outcome** of interest is retention on buprenorphine treatment or remaining engaged in buprenorphine treatment over a 3-month period. We hypothesize that

participants receiving the PPMI condition (intervention condition) will have higher levels of retention on buprenorphine treatment over the 3-month follow-up period when compared to participants who receive the EUC condition (control condition). For **Primary Aim 1**, retention on buprenorphine treatment will be measured using data collected from the weekly surveys and the Time Line Follow Back (TLFB). Participants will have the opportunity to complete a total of 13 surveys over the course of the first 13 weeks of the study. During these weekly surveys, participants will be asked to respond to three questions that will be used to measure treatment retention: (1) a dichotomous questions regarding treatment engagement status (“Are you still being prescribed buprenorphine as a treatment for problematic opioid use?”); (2) a question regarding number of days that the participant has taken their medication recently (“On the calendar below, please check off each day that you have taken your buprenorphine out of the past 7 days.”); and (3) a dichotomous question regarding overall buprenorphine treatment engagement since the beginning of the study (“Since you began this study on ____ {DATE} ____, has there been any time when you went for at least 7 days at a time WITHOUT taking your buprenorphine for any reason?”). Data from these weekly surveys is expected to have greater specificity than data collected during the follow-ups due to the nature of the data collection (i.e. each week versus retrospectively over several months). This weekly survey data will be utilized to guide the discussion of the TLFB during the 1- and 3-month follow-up in order to ensure all data is captured. The main outcome measure used for data analyses, therefore, will be the TLFB.

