The primary outcome measure for this study is retention on buprenorphine treatment as measured over 3-months. Secondary Aim 1 for this study is retention on buprenorphine treatment over 12-months. This will be operationalized as time to first episode of buprenorphine treatment non-adherence. Non-adherence, or discontinuation of treatment, will be defined as a consecutive period of 7 or more calendar days without taking buprenorphine. Buprenorphine retention will be collected in a variety of ways for this study:

- (1) as part of the TLFB assessment, which will be administered at the baseline enrollment assessment and the 1-, 3-, 6-, 9-, 12-month follow-ups in which the participant will be asked to recall on which days they took their buprenorphine medications;
- (2) as part of weekly surveys completed during the study;
- (3) through medical record reviews at the treatment sites (as applicable when participants and clinics have provided proper releases of information) to review urine toxicology screens and/or prescription fill records;
- (4) through urine analysis at 1-, 3-, 6-, 9-, and 12-month follow-up

Medical Records will be reviewed, when applicable, for the following piece of information regarding buprenorphine treatment: (1) number treatment appointments scheduled with the buprenorphine provider, (2) number of treatment appointments completed with the buprenorphine provider, (3) number of treatment appointments scheduled but not completed by the participants with the buprenorphine provider, (4) urine toxicology results obtained as part of buprenorphine treatment only, (5) prescription fills for buprenorphine prescriptions through the VA pharmacy. The research team has extensive experience obtaining prescription fills and other data through CPRS from prior studies.

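### Section 6.2.3 lists project managers as blinded outcome collectors although they randomise every participant, and denies staff involvement in a 3-month outcome whose main measure is a staff interview

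*Combined protocol and SAP*

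**What the plan says.** On who knows the assignment, section 6.2.2 (Randomization) says: "Research staff will contact the project managers to randomize all participants using the randomization sequence provided by the biostatistician". It continues: "The randomization process will be overseen by the project managers who will be notifying the research therapists of assigned" condition, participant by participant, once baseline is complete. Section 4.3 adds that project managers, with the principal investigators and the biostatistician, monitor the balance of assignments.

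On who is blind, section 6.2.3 says: "Data collectors responsible for the collection of follow-up data (post-enrollment data) (i.e. research assistants, project managers, or other study staff) will remain blind" to assignment.

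On the source of the 3-month primary outcome, section 6.2.3 gives weekly self-report surveys and concludes: "Therefore, study staff will not be directly involved in the collection of those outcome data". Section 9.5.1 gives the surveys a supporting role: "This weekly survey data will be utilized to guide the discussion of the TLFB during the 1- and 3-month follow-up". It then says: "The main outcome measure used for data analyses, therefore, will be the TLFB".

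**The concern.** Participants and therapists know the condition (section 6.2.3), and section 9.5 says all outcomes are patient-reported. The primary event is the first run of 7 or more days without buprenorphine, and its date comes largely from guided recall in an interview. Blinding the person who leads that recall is therefore one of the main protections against recording events differently in the two arms.

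Section 6.2.3 weakens that protection in two ways. It lists as blind a role that cannot be blind, so a person who knows the assignment could conduct the interview without departing from the collector list. It also reassures the reader that staff do not touch the 3-month outcome, so no one is prompted to ask who does the 1- and 3-month interviews.

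**Working it through.** No figure in the plan is at stake, so the check compares the sections.

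**Part 1: can project managers be blind?**

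1. They carry out randomisation for all participants from the biostatistician's sequence (6.2.2).
2. They pass the assigned condition for individual participants to the therapists (6.2.2), so they know it at participant level.
3. They watch assignment balance during the trial (4.3).
4. Section 6.2.3 includes them, in a list introduced by i.e., among the follow-up collectors who stay blind.
5. I found no section that divides the role, for example into a project manager who randomises and another who interviews.

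Steps 1 and 2 alone are incompatible with step 4 for any project manager who does both jobs.

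**Part 2: where does the 3-month primary outcome come from?**

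| Section | Source given | Staff involvement |
|---|---|---|
| 6.2.3 Blinding | Weekly self-report surveys | Said to be none directly |
| Précis, Design and Outcomes | Weekly surveys and TLFB | TLFB is a research interview |
| 9.5.1 Primary Outcome | Both; TLFB is the main measure | Surveys guide the TLFB interview |
| 9.6 Data Analyses | TLFB and surveys, compared with each other | TLFB as above |
| 6.2.2 Baseline Assessments; 9.5.1 | TLFB | Administered by an interviewer |
| 6.2.4 Weekly Surveys | Surveys online or by phone | Research assistants read and record phone surveys |

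Section 9.5.1 fixes the timing of the buprenorphine recall: "as part of the TLFB assessment, which will be administered at the baseline enrollment assessment and the 1-, 3-, 6-, 9-, 12-month follow-ups". Two of those visits, at 1 and 3 months, fall within the primary period.

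Section 6.2.3 contrasts the 3-month outcome, said to need no staff, with the 12-month outcome, collected by interview and therefore by blinded staff. The contrast fails, because section 9.5.1 uses the same interview as the main measure at 3 months. The protocol's own reason for blinding the later interviewers applies equally to the earlier ones.

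**Extent.** Scheduled TLFB follow-up interviews in the primary period: 200 participants × 2 visits = 400. At the 80% follow-up that section 4 expects (n = 160), 160 × 2 = 320. These count all scheduled interviews, not those done by project managers. The documents give no share for project managers and no estimate of differential recording, so the calculation stops here.

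**The case against.** The best defence is that the general sentence in 6.2.3 already blinds everyone who collects post-enrolment data, which includes the 1- and 3-month TLFB and the phone surveys. On that reading, a project manager who collects no follow-up data breaks no rule. No section assigns TLFB interviews to project managers, the plural leaves room for a split of duties, and the Manual of Operations and SOPs, not available here, may make one. This stands as a limit: the documents do not show that an unblinded interview will take place. It does not remove the contradiction, because 6.2.3 names the role and states no separation.

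It is also fair that the weekly surveys are a real source for the outcome (Précis, 9.5.1, 9.6). Section 6.2.3 is therefore incomplete rather than wholly wrong about the source. Its conclusion that staff are not directly involved is still wrong.

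Other protections exist. Adjudicators, data managers and analysts are to be blind, and sources are compared. They help only in part: blind analysts cannot undo differential recording, and 9.6 gives no rule for reconciling sources. Urine tests are voluntary and are not primary outcome data (6.2.4). Buprenorphine has a listed maximum detection time of 2-3 days (6.2.2), so a visit test cannot date an earlier 7-day gap.

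A reader might infer three stronger points that the documents do not support:

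- **Allocation concealment is broken**, because project managers may take consent (6.2.1) or receive eligibility questions (4.3). Section 6.2.2 keeps enrolling staff out of sequence generation, password-protects the sequence and randomises after baseline. No breach is shown.
- **Adherence review shows project managers each participant's arm.** Section 9.2.1 says "Adherence of participants will be evaluated by the Project Managers", but the context is whether adherence falls below the expected rate. The contradiction does not need this step.
- **The type I error is inflated by a known amount.** Any such figure needs an assumed share of interviews and an assumed recording bias, and the documents give neither.

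**Conclusion.** Both inconsistencies hold on the current text. Section 6.2.3 claims blinding for a role that sections 6.2.2 and 4.3 give the assignments to, and it denies staff involvement in an endpoint whose main measure is an interview. This should be fixed, because the endpoint is self-reported in a trial where participants and therapists are unblinded.

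The conclusion is confined to what is written. The 1- and 3-month interviewers are nominally blind, and a reader should not conclude that they are unblinded or that the results are biased. The size of any bias is unknown. The finding rests on one assumption: that no operational document already separates assignment holders from interviewers. If one does, the remedy is to say so in the protocol.

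**What to change.** In section 6.2.3:

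- **(a)** Remove project managers, and any other staff who randomise, notify therapists or otherwise know assignments, from the list of blinded collectors. State that they do not conduct follow-up interviews or phone weekly surveys.
- **(b)** Replace the sentence denying direct staff involvement. Say that the 3-month primary outcome uses the interviewer-administered TLFB as main measure, guided by and compared with the weekly surveys, in line with 9.5.1 and 9.6. Add that the 1- and 3-month TLFB interviews and phone weekly surveys are done only by staff without access to assignments or session records.

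The cost is protocol and SOP wording and a small loss of flexibility, since project managers could not cover follow-up interviews. Staffing numbers are not given, so the extra load on other interviewers cannot be stated.

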Zoom) will be recommended and encouraged. The initial enrollment appointment will be scheduled to be completed remotely over the phone or via video chat, however a participant may request an in-person meeting at a time and place that is convenient for the participant (e.g. the treatment clinic, their home, or a mutually agreed upon community location such as a restaurant, coffee shop, or library). These options will be discussed with all participants who have screened eligible and interested in participating in the study. Eligibility status for all participants will be documented in the Screening Eligibility Log as well as the Screener Inclusion-Exclusion Case Report Form. Information included in these documents will include the recruitment site the participant was recruited from, the type of recruitment (in-person, phone, e-mail, letter, website, newsletters, referral, etc.), and the eligibility status. The Inclusion-Exclusion Case Report Form must be completed prior to enrolling the participant into the full RCT in order to ensure that all inclusion criteria have been met and no exclusionary criteria exist. Any questions regarding study eligibility will be directed to the Project Managers and/or PIs prior to the consent and enrollment of the potential participant into the trial. The Inclusion-Exclusion Case Report Form will also be reviewed and monitored by the Project Managers for accuracy and completeness on a regular basis.

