Once a participant has provided informed consent, they may begin the baseline assessment with the research administered interview to confirm eligibility (e.g. the presence of an OUD diagnosis of at least mild severity within the past 12 months as measured by the Structured Clinical Interview for DSM-5). Participants will not be considered enrolled in the trial until full eligibility has been confirmed. Those who do not meet criteria for a diagnosis of an OUD of at least a mild severity within the past 12 months will be notified they are not eligible for the RCT, thanked for their time, and receive study payment for the assessment. Eligible participants will continue and complete the remaining parts of the baseline assessment, be considered enrolled into the trial, and will be eligible for randomization. Following the completion of all baseline study activities, participants will be randomly assigned to either the PPMI or EUC conditions. Stratified random assignment to intervention (PPMI) and control (EUC) conditions will be employed by gender (operationalized as biological sex assigned at birth), past year use of heroin (yes/no), and veteran status (community/veteran). While utilizing multiple randomization blocks can complicate the enrollment process, there is evidence that the trajectories of treatment retention and outcomes varies between men and women, as well as between those with history of heroin use versus those without heroin use. The project biostatistician will guide the randomization process. To prevent the possibility that staff could unwittingly manipulate patient assignment to treatment, a computerized randomization technique will be used, wherein the odds of treatment assignment change, based on the immediately preceding assignments, but odds are not truly fixed, as in strict balancing. Sequential runs of assignment to one condition are possible but are equalized by the end of a randomization block of participants. Randomization to conditions will be monitored by the Project Managers in conjunction with the project PIs and biostatistician to ensure that conditions remain balanced and will revisit the blocking procedures should any imbalances occur during the trial.

Secondary Aim 4: Enrollment of participants and providers for qualitative interviews

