6.2.1 Screening Evaluation

Potential participants will be recruited to participate in the eligibility screening in a variety of ways. For details, please refer to Section 4 “Selection and Enrollment of Participant” above, specifically subsection 4.3 “Study Enrollment Procedures”. Results of all record reviews, in-person, online, and phone recruitment outcomes will be documented in the Screening Eligibility Log.

Consenting Procedure

A general description of the consent process is described above in Section 4.3 “Study Enrollment Procedures”. In summary, this study will have a two consent process in which consent will be obtained prior to the completion of the eligibility screening, and a second consent will be obtained from participants prior to their enrollment into the full RCT. Trained research staff will conduct the informed consent processes. For this study, the informed consent process may be conducted by a study project manager, the research

assistants, or the study therapists. All research staff will have received training by the investigators, project managers, and/or the IRB coordinator regarding the consenting process. Trainings may include but are not limited to: attending specialized trainings regarding informed consent in research, role plays, quizzes, and handouts regarding the informed consent process. Training topics will include going over the components necessary in consenting, the voluntary nature of the study, importance of properly consenting individuals, rights of participants to withdraw from the study, etc.

Before a potential participant completes the eligibility screening survey to determine initial study eligibility, electronic or verbal consent will be obtained. A request for a waiver of documentation of informed consent has been requested from the IRB for this eligibility screening process. For those participants who are eligible and agree to participate in the full RCT, full informed consent will be obtained before the participant engages in further study activities. Before moving onto the eligibility screening survey, participants will have the ability to print, save a copy of the electronic consent information sheet, or be provided a paper copy if requested. Those who complete the eligibility survey via phone may have the consent information sheet mailed or e-mailed to them if requested.

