Following completion of all data collection during the baseline assessment, participants will be randomized to a treatment condition – Psychosocial Pain Management Intervention (PPMI; n=100) or Enhanced Usual Care (EUC; n=100). Randomization to condition will be carried out blocking on gender (biological sex; male versus female), past year use of heroin (yes/no), and veteran status (community/veteran). Participant responses to questions based on biological sex and opioid use history obtained during the eligibility screening survey will be utilized to select the appropriate block for randomization. Research staff will confirm the participant responses before beginning the randomization procedures. “Gender” for randomization purposes will be operationalized as the biological sex the participant indicated they were assigned at birth. Additional questions regarding the gender the participant identifies with will also be collected but will not be used for randomization purposes. Should a participant decline to answer a key blocking variable during the survey administration, research staff will verbally ask clarification questions to determine block assignment. If a participant refuses to provide the necessary information that allows for the possibility of blocking, they will be excluded from participating further in the study.

Computerized randomization will occur in blocks of randomly chosen sizes in order to equalize randomization over time and to prevent the possibility that staff could unwittingly manipulate subject assignment to conditions. The study biostatistician will complete the treatment allocation sequence process prior to the start of recruitment for the study. Staff members who will be involved in the enrollment process will not be included in the randomization sequencing process. To further avoid manipulation of condition, randomization will not be determined until after all baseline data collection activities have been completed. We will utilize allocation concealment procedures to ensure that that research staff member enrolling the participant will not know in advance which treatment the next person will receive.

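### As written, allocation concealment is not protected from the project managers, who randomise from the sequence and may also take consent and receive eligibility queries

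*Combined protocol and SAP*

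**What the plan says.** Section 6.2.2 makes two undertakings. The first is "Staff members who will be involved in the enrollment process will not be included in the randomization sequencing process". The second is that concealment procedures will keep the enrolling staff member from knowing the next assignment beforehand.

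The same section then describes the mechanics. "The study biostatistician will complete the treatment allocation sequence process prior to the start of recruitment for the study". The documents holding the sequence are password protected against inadvertent access by enrolment staff. After that, "Research staff will contact the project managers to randomize all participants using the randomization sequence provided by the biostatistician", and "The randomization process will be overseen by the project managers who will be notifying the research therapists of assigned" condition.

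Elsewhere the project managers are given a part in entry:

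- Section 4.3: "Any questions regarding study eligibility will be directed to the Project Managers and/or PIs prior to the consent and enrollment". They also review the Inclusion-Exclusion form regularly for accuracy and completeness.
- Section 6.2.1: "the informed consent process may be conducted by a study project manager", as well as by research assistants or study therapists.
- Section 4.3: the project managers, working with the PIs and the biostatistician, monitor balance between conditions and "will revisit the blocking procedures should any imbalances occur during the trial".
- Section 10.1: they periodically look at eligibility criteria, recruitment numbers and the randomisation tables.

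**The concern.** Allocation concealment requires that nobody who influences whether or when a person enters the trial can know the arm that person would receive. Here one role both works from the list and has a possible hand in entry. Someone who can see the next slot in a stratum could, without intending to, admit, query or defer a candidate according to that slot.

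Little later in the trial would repair such selection. Section 6.2.2 leaves people who are not randomised out of the study, so an intent-to-treat analysis of those who were randomised cannot reveal or correct steering. Adjusting for the stratification factors does not remove it either. Participants and therapists are unblinded (section 6.2.3) and all outcomes are patient-reported (section 9.5), so the comparison depends heavily on a clean allocation.

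**Working it through.** The plan gives no figure on this point, so the check is to set the sections side by side.

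**1. Could a project manager know the next assignment?** The sequence is complete before recruitment, is kept in documents, and is used by the project managers for every participant (section 6.2.2). Section 10.1 has them look at randomisation tables. In a pre-generated stratified list, the next slot in each of the 8 strata (section 3) is fixed at any moment. The answers on sex and opioid use history that select the stratum come from the screening survey (section 6.2.2), so much of what identifies a candidate's slot is known before enrolment. Advance knowledge is therefore strongly implied. No section says outright that project managers can open the list ahead of need.

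**2. Do project managers take part in entry?** Yes, in two ways. They may conduct consent (section 6.2.1), and they receive eligibility queries with the PIs before consent (section 4.3). Their review of the Inclusion-Exclusion form reads as quality control, and I give it no weight.

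**3. Do the stated safeguards bind someone working from the list?**

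- Password: aimed at enrolment staff, not at those who use the sequence.
- Random block sizes: these hinder guessing, not reading.
- Randomisation only after baseline: this governs when an assignment is revealed, not whether the next slot already exists.
- Computerised technique (sections 4.3 and 6.2.2): section 6.2.2 still describes a sequence generated in advance and provided for use. Release of one assignment at a time with later ones hidden is not described.

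**4. Which entries are exposed?**

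| Route of entry | Concealment as written |
|---|---|
| Research assistant enrols, no eligibility query | Holds |
| Eligibility query answered by a project manager | Not protected |
| Project manager takes consent | Not protected |

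Project managers execute all 200 assignments, but only the second and third routes are exposed. The documents do not say how many entries follow them.

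**5. Balance monitoring.** The project managers and PIs see running balance and, with the biostatistician, may alter the blocking. People with a role in entry thus receive information by arm and can take part in changing the scheme mid-trial.

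**The case against.** The strongest reply is that this is silence, not failure. Section 6.2.2 says concealment procedures will be used without describing them, and section 4.3 defers enrolment steps to the Manual of Operations and site procedures, which may close the gap. The biostatistician generates the sequence. Section 6.2.2 treats the project managers as distinct from the staff who enrol. Most entry criteria are rule-based, such as a pain score of 4 or more, a SCID-5 diagnosis and a dose within 10 days. Queries go to the project managers and/or the PIs, and the PIs have final discretion (section 4.2).

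Much of this stands, and it rules out several stronger readings that a reader might infer:

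- *Concealment fails for the whole trial.* Not supported. Look-ahead access is inferred, and entry by a research assistant without a query remains concealed.
- *The separation sentence is breached.* Not clearly. It follows directly on generation of the sequence and most naturally refers to generation, which is kept separate. The conflict is with the concealment promise.
- *Project managers make the judgement calls on competence and intoxication.* The text gives these to research staff, with clinician investigators consulted on the exclusion decisions (sections 4.2 and 4.3).
- *The blocking can be changed without statistical input.* Section 4.3 includes the biostatistician.
- *A bias can be sized.* Suppose 5% or 10% of each arm's places were steered between people at 75% and 25% risk of drop-out, in opposite directions by arm, with no true effect and 50% drop-out. Each arm shifts by 0.05 × 0.5 = 0.025 or 0.10 × 0.5 = 0.05. The apparent hazard ratio is ln(0.525)/ln(0.475) = 0.87 or ln(0.55)/ln(0.45) = 0.75. The steered share and both risks are invented, so these values are not estimates for this trial.

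What the reply does not remove is that the protocol gives the same people list use, permission to take consent and a place in the query route, with no rule keeping these apart.

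**Conclusion.** The point holds in a limited form. For any participant whom a project manager consents, or whose eligibility query a project manager answers, the protocol does not secure the concealment that section 6.2.2 promises. This assumes that using the sequence gives sight of later slots, which the text implies without stating, and that the unseen operating procedures add no barrier. The number of exposed entries is unknown, and neither the size nor the existence of bias can be derived from the documents. It should be fixed because the remedy changes who holds the list and who decides entry, and it is cheap. The documents do not show that allocation has been compromised.

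**What to change.** 1. Custody: the biostatistician, or a computerised system that hides future assignments, holds the sequence. One assignment is released only after consent, the Inclusion-Exclusion form, the stratum and baseline are locked.
2. Roles: state that nobody who can view the sequence may take consent or decide an eligibility query. Send queries to a PI without list access.
3. Blocking: keep the scheme fixed, with balance by arm reviewed by the biostatistician only. Delete the option to revisit it.
4. If enrolment is complete: document and report who could view the sequence, and whether those people took consent or decided eligibility.

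The cost is an edit to the protocol and Manual of Operations and a change in who holds the file. It needs no extra staff. The downside is a short wait for each assignment if release is not automated.
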